## **A. Specific Aims/Objectives**

1. To observe how concussion affects cerebrovascular function and symptoms among adolescents.
2. To investigate the effect of a sub-maximal exercise protocol on cerebrovascular function and concussion symptoms in adolescents who have recently sustained a concussion.

## **B. Background and Significance**

An estimated 1.6 to 3.8 million sport-related traumatic brain injuries occur annually in the United States, the vast majority being concussions. Despite this high prevalence, the clinical management of concussion remains difficult. Recovery of symptoms following a concussion usually occurs within a few days to a few weeks of injury. These symptoms, which include cognitive difficulties, headache, and dizziness, are pervasive, impacting personal relationships, community re-integration, return to sports, and the ability to work or go to school. Unfortunately, the pathophysiology of persistent concussive symptoms remains poorly understood, and very few treatment options are available.

After concussion, optimal cerebral blood flow is necessary to meet the metabolic needs of the injured brain. However, cerebral blood flow is diminished globally after injury, and in fact, there may be an inverse relation between regional flow and symptom burden after concussion. Thus, cerebrovascular dysfunction may play a role in the manifestation of prolonged concussive symptoms. Moreover, alterations in cerebral perfusion may act as a trigger in symptom exacerbation. Even if overt symptoms are mostly gone, strenuous effort may induce symptoms, presenting a major obstacle to return to daily activities. However, prolonged cessation from physical activity may also induce concussion-like symptoms, such as difficulty sleeping, concentration abnormalities, and anxiety.

While high intensity exercise can induce symptoms after a concussion, mild to moderate (so-called sub-maximal) exercise has recently been identified as a safe activity after a concussion. Recent investigations have supported the use of sub-maximal exercise protocols to improve patient outcomes following concussion, and have identified that more physical activity following a concussion is not universally detrimental to the duration of time required for symptom resolution. Therefore, it is conceivable that mild-to-moderate exercise can contribute to symptom resolution by improving cerebrovascular function, while avoiding symptom exacerbation associated with high-intensity exercise. Although the 2013 recommendations for concussion in sport states that individuals should remain at-rest until asymptomatic, these guidelines are expected to change in 2017. This is due to recent evidence regarding exercise after concussion that suggests early exercise may not be detrimental, and perhaps beneficial in the early stages of recovery (i.e. within 10 days of injury). Specifically, some researchers and clinicians now suggest tailoring management plans to individual signs and symptoms based on the patient's most bothersome findings in order to move away from "one therapy for all" treatments. Therefore, early exercise interventions at a sub-maximal level soon after concussion may be a beneficial strategy in reducing the risk of persistent symptoms.

## **D. Design and Methods**

### **(1) Study Design**

Prospective, non-blinded, Interventional study

We plan to recruit up to 60 concussed patients, equally randomized to an intervention group who participate in the at home exercise program, or those who undergo the same testing but receive the standard of care given by their physician. Subjects will be recruited from Boston Children's Hospital Sports Medicine Clinic, The Micheli Center for Sports Injury Prevention as well as affiliated schools, clinics and sports organizations. The subjects and parents/guardians who voluntarily agree to participate will be scheduled for three visits. Upon the first visit, a research coordinator will explain the study and have the subject and parent/guardian sign the "Research Consent Form", approved by the Institutional Review Board of Boston Children's Hospital before participating in the study. Subjects will be required to complete three visits to The Micheli Center for Sports Injury Prevention or Spaulding Hospital in Cambridge for testing.

## **(2) Patient Selection and Inclusion/Exclusion Criteria**

### **Inclusion**

- Male or females between 14-21 years of age
- Experienced a concussion within 14 days of testing, defined as a person who has had a traumatically induced physiological disruption of brain function, manifested by at least one of the following:
  - Any period of loss of consciousness;
  - Any loss of memory for events immediately before or after the accident;
  - Any alteration in mental state at the time of the accident (ie., feeling dazed, disoriented, or confused)
  - Symptoms of nausea, dizziness, fatigue, headache, or changes in sleep, cognition or, emotions following the accident
- Low or moderate cardiac risk according to American College of Sports Medicine (11)

### **Exclusion**

- History of neurological surgery
- Seizure disorder
- Use of medication or medical device that would alter heart rate, blood pressure or autonomic function
- Any current, serious, chronic medical or psychiatric disease that, in the Principal Investigator's judgment, may interfere with study participation or data integrity
- Unable or unwilling to provide informed consent

## **(3) Description of Study Treatments or Exposures/Predictors**

Concussion Symptoms will be monitored by the Post-Concussion Symptom Inventory (PCSI), Post-Concussion Symptom Score (PCSS), the abbreviated Concussion Symptom Inventory (CSI), and Visual analog scale (VAS)

Surveys: Dizziness Handicap Scale, Hospital Anxiety and Depression Scale (HADS), Patient Health Questionnaire (PHQ) will be completed before each testing visit.

Height and weight will be measured.

Heart rate, cerebral blood flow, and end-tidal CO2 will be recorded during a one hour session, before graded exercise test, during a graded exercise test on a cycle ergometer, and during 5 minutes of recovery. The branching exercise protocol (shown in Figure 1 below) based on the modified YMCA protocol will progressively increase exercise intensity up to 85% of age-predicted maximum heart rate. Exercise will be stopped at this point or if the volunteer becomes symptomatic.

Single/ Dual-Task Gait: Patients will be instrumented with three accelerometer devices, attached via elastic strap at L5, left, and right feet, which take less than one minute to place on the patient. The devices will be wirelessly connected to a laptop run by the study coordinator to obtain and save motion data. While wearing these devices, they will complete tasks in three different conditions:

- *Standing single-task:* patients will be seated and be asked to complete a mini-mental status examination, adapted from previous investigations and recommendations. It consists of spelling a five letter word backwards, serial subtraction of 6s or 7s, or reciting the months in reverse order. 8 trials will be completed.
- *Walking single-task:* patients will be instructed to walk down the hall at a length of 10m, turn around and return to the original starting point, with no obstruction or completion of other tasks. 8 trials will be completed.
- *Walking dual-task:* patients will be instructed to walk down the hall at a length of 10m, turn around and return to the original starting point, while completing a mental status examination. The examiner will ask the patient to spell a five letter word backwards, subtract by 6s or 7s from a number, or recite the months in reverse order. The examiner will say, "Ready, go" and the patient will begin walking while completing the mental task. 8 trials will be completed.
- *Static postural stability:* As the Balance Error Scoring System (BESS) test is typically performed as a part of the clinical exam, participant performance will also be documented. During the BESS, three experimental trials are performed with eyes closed in 3 conditions: double-leg stance, single-leg stance, and tandem stance. During double-leg stance, participants are instructed to stand with their feet positioned side by side. For the single-leg stance condition, participants stand on the foot that they identified as their non-dominant kicking leg. The tandem stance condition consists of participants standing with their feet positioned where the non-dominant foot is placed directly behind the dominant foot. Each trial is performed for 20 seconds. When available, participants will perform the test on an instrumented motion capture-force platform system.

Estimated time to complete the single and dual-task balance assessment is approximately 8 minutes. The order of assessments will be rotated for each visit, but consistent for all subjects.

Heart rate will be monitored via a standard 5-lead ECG.

Cerebral blood flow will be monitored via Near-Infrared Spectroscopy (NIRS) and transcranial Doppler ultrasound (TCD). NIRS will be measured with a probe placed on the forehead contralateral to the dominant hand. NIRS-derived blood oxygenation levels will be used as a measure of cerebral blood flow at the prefrontal cortex. TCD will be measured with probes placed bilaterally on both sides of the head slightly behind the temples. TCD derived blood flow velocities on middle cerebral arteries will be used as a measure of global cerebral blood flow. The TCD protocol used will be exactly the same as the active and IRB-approved protocol (Protocol number: 8926) within this study.

Arterial blood pressure will be monitored continuously via a photoplethysmographic finger cuff on the index or middle finger throughout the study session and via a standard oscillometric blood pressure cuff attached to the upper arm. Pressure measurements will be obtained only via oscillometric blood pressure cuff during the graded exercise.

[figure not shown]
End-tidal CO2 will be monitored using infrared analyzer (Model 17515A, VacuMed) connected to a nasal cannula.

Rate of Perceived Exhaustion (RPE) will be monitored by a visual Borg rating of perceived exertion during the graded exercise test

All aerobic activity will be monitored by a Polar Wrist Units with Heart Rate Monitors.

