**Figure 1: Modified sub-maximal exercise protocol**

#### **(4) Definition of Primary and Secondary Outcomes/Endpoints**

- Primary: blood oxygenation level in the prefrontal cortex before and after the administration of the exercise protocol.
- Secondary: the proportion of participants who continue to experience symptoms after the 8-week exercise intervention and the potential confounding variables that contributes to this risk of persistent symptoms.

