#### Study Visit 3 (8 weeks post-enrollment):

All subjects will participate in this visit (usual care and intervention). Subjects will undergo the same procedures as visit one, including completing the DHS, HADS, PHQ, PCSI/PCSS, cerebrovascular function tests, graded exercise test, VOMS and single/ dual-task gait.

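### Gait and balance task order changes by visit but is the same for every participant, so within-group or pooled change over visits cannot be separated from an order effect

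*Combined protocol and SAP*

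**What the plan says.** Section D(3) describes a gait battery in which "they will complete tasks in three different conditions" (a cognitive task alone, walking alone, and walking with a cognitive task, 8 trials each), followed by the BESS balance test. It then gives a duration, "Estimated time to complete the single and dual-task balance assessment is approximately 8 minutes", and the next sentence is the order rule: "The order of assessments will be rotated for each visit, but consistent for all subjects".

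The rest of the design is relevant in four ways:

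- **Visits and arms.** Section D(1) says "Subjects will be required to complete three visits" and "We plan to recruit up to 60 concussed patients, equally randomized to an intervention group", the comparator being standard of care. The Schedule in D(5) has both arms attend all three visits.
- **Endpoints.** D(4) gives "Primary: blood oxygenation level in the prefrontal cortex before and after the administration of the exercise protocol". The secondary endpoint concerns persistent symptoms. Neither is a gait or balance measure.
- **Analysis.** Section H describes one mixed model, for regional cerebral blood flow. It has no order term and no gait or balance outcome.
- **Place of gait in the session.** The data collection list in D(5) puts gait testing at rest ahead of exercise. The Visit 1 schedule puts it last, after the graded exercise test.

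**The concern.** Rotation protects against order effects when different participants meet the tasks in different orders at the same time point. Under this rule nobody does. Everyone has one order at Visit 1, another at Visit 2 and a third at Visit 3, so a task's position is a fixed function of visit. Any fatigue, practice or symptom provocation that depends on position adds directly to the visit effect for that task.

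An order effect is plausible here, because the same kinds of mental task appear in both the cognitive-only and the dual-task condition, with 8 trials of each. The study enrols only concussed patients, so an account of recovery in gait or balance would rest on change over visits, which is the contrast affected. The data will be collected from every participant at three visits, and the problem cannot be undone afterwards.

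**Working it through.** The documents state no figure on this point, so there is none to reproduce. The check has three parts.

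**1. Is order separable from visit?** Inputs from the protocol: 60 participants (the planned maximum), 1:1 allocation, 3 visits, one order per visit. Assumption: three tasks, so a given task takes a different one of three positions at each visit. The table gives the rank of the design matrix for one task's score.

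| Terms | Rank |
|---|---|
| Participant (60) + visit (2) | 62 |
| The same + order position (2) | 62 |
| Participant + visit + arm-by-visit (2) | 64 |
| The same + order position, protocol's rule | 64 |
| The same + order position, counterbalanced across participants | 66 |

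Under the protocol's rule the order terms add nothing to the rank: they are aliased with visit. Arm-by-visit adds its full 2 and stays estimable. With counterbalancing, both order contrasts become estimable (66 − 64 = 2).

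**2. Which contrasts are biased?** Let *o* be the order effect between two visits, *t* the true change and *d* the true arm effect on change. The expected change is *t + o* under usual care and *t + o + d* in the exercise arm. The within-arm change carries *o*. The difference between arms is (*t + o + d*) − (*t + o*) = *d*. A simulation of 5,000 trials agrees. It assumed order effects of 0, 0.5 and 1.0 SD at Visits 1 to 3, no true change, and *d* = 0.5 SD. The mean Visit 1 to 3 change in the control arm was 1.01 SD against a true 0; the mean between-arm difference was 0.49 SD against a true 0.50.

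**3. How large could the consequence be?** This part is illustrative only. Assume a pooled paired t-test at two-sided 0.05, 60 complete pairs, no true change, order effect *o* in SD units and between-visit correlation *r*.

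SE of the mean change = √(2(1 − *r*)) / √60, and the noncentrality is *o* / SE. At *r* = 0.7, SE = √0.6 / √60 = 0.10. Then *o* = 0.3 gives noncentrality 3.0, and *o* = 0.2 gives 2.0. Probability of falsely declaring change, from the noncentral t with 59 degrees of freedom:

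| Assumed order effect | r = 0.5 | r = 0.7 | r = 0.8 |
|---|---|---|---|
| 0 | 5% | 5% | 5% |
| 0.1 SD | 12% | 17% | 23% |
| 0.2 SD | 33% | 50% | 67% |
| 0.3 SD | 63% | 84% | 95% |

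**The case against.** The strongest objection is that no planned inference is touched. The order rule directly follows the 8-minute estimate for the gait and balance tasks, and those tasks are not an endpoint in D(4) and have no analysis in section H. The pooled paired test behind the table is not in the plan. This stands. It makes the measures exploratory in effect, and the error rates illustrations rather than properties of a planned test.

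A reader might infer that Aim 1 is compromised, since it is observational and there is no uninjured group. The documents do not support that. The aim is "To observe how concussion affects cerebrovascular function and symptoms among adolescents"; gait and balance are not in it. The surveys are completed before each testing visit, the Visit 1 schedule sets out the cerebrovascular and exercise parts in sequence, and later visits repeat the same procedures. Aim 1 would be drawn in only if the rotation covered the whole session. The protocol does not define the scope, but that is not its natural reading.

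A reader might also infer that all change over time is uninterpretable. That too goes beyond the design: both arms share the same order at each visit, so the randomized comparison of change survives. Only an order effect that differs between arms would bias it.

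Finally, rotation has a use. For a single-task versus dual-task contrast, it moves each task through different positions over the visits, whereas one fixed order ties task to position every time. That is fair, and it is why a fixed order is not the preferred remedy below. Counterbalancing across participants keeps this benefit without the confounding.

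**Conclusion.** The point holds for within-group and pooled change over visits in the measures that rotate, most naturally gait and balance. For these, order and visit are completely aliased. That conclusion needs no assumption beyond the stated rule; the size of any bias depends on an order effect that the documents do not give. At an assumed 0.2 to 0.3 SD with correlation 0.7 and 60 complete pairs, a pooled paired test would be wrong in about 50% to 84% of studies with no true change. Near zero effect it would be wrong in about 5%. Since enrolment is only up to 60, complete pairs may be fewer, which would lower the upper figures.

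The between-arm difference in change is not biased by a common additive order effect. On the natural reading of the rule, the primary endpoint, the secondary endpoint and the section H model are unaffected. This is a minor design flaw, worth correcting because the correction is cheap before data collection and impossible after it.

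**What to change.** 1. Replace the order rule in D(3). Assign each participant an order sequence from a Latin square, balanced within arm, so that every order is in use at every visit. With three sequences and 30 participants per arm, that is 10 per sequence in each arm.
2. Include order position in any model of these measures.
3. State which assessments the rotation covers, and whether BESS is one of them.
4. Reconcile the data collection list in D(5), which has gait at rest before exercise, with the Visit 1 schedule, which has it in the final part after the exercise test.

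The cost is a pre-printed order list, slightly more attention from testers, and two extra model terms for three positions.

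One fixed order at all three visits is a weaker alternative. It removes order differences between visits, but it confounds task with position and leaves practice across visits in place. If the present rule is kept, inference on these measures should be limited to the between-arm difference in change.

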***Data collection methods:***

Height/Weight

Cerebral blood flow: NIRS and TCD systems

CO2 levels obtained during the study session and exercise

Blood Pressure obtained during the study session and exercise

Heart Rate: 5 lead ECG during the study session and exercise

Rate of Perceived Exhaustion: Borg Scale

Post-concussion symptom inventory: PCSI, PCSS, CSI

Single/ dual-task gait assessments at rest before exercise

Aerobic Activity: Polar Wrist Units with Heart Rate Monitors

Anxiety, Dizziness and patient health surveys are measured by the following scales: Dizziness

Handicap Scale (DHS), Hospital Anxiety and Depression Scale (HADS), Patient Health Questionnaire (PHQ)

The protocol consists of measurements and procedures that have no known risks and have been routinely used in laboratory studies as well as other human physiology and biomechanics labs without any adverse events. Throughout each examination, the electrocardiogram will be monitored using a standard 5-lead ECG via wires attached to the chest via hypoallergenic adhesive electrodes. Blood pressure will be monitored every 2 – 4 minutes via a standard oscillometric blood pressure cuff attached to the upper arm, and monitored continuously via a photoplethysmographic finger cuff on the index or middle finger.

The attachment and removal of ECG electrodes and inflation of the blood pressure cuff may cause mild discomfort (though no more than routine physical examinations), but there are no risks associated with any of these measurements.

Cerebral blood flow will be measured via ultrasound with a Doppler probe placed on the left and right temple and a NIRS probe placed on the forehead contralateral to the dominant hand. There are no known risks associated with transcranial ultrasound or near infrared spectroscopy. We routinely use both (currently, in over 50 young individuals) with no reported discomfort or ill effects.

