***Schedule:***

Recruitment: Potential concussed subjects will be recruited from the sports medicine clinic at Boston Children's Hospital by a research staff member. If the subject is eligible and interested in participating they will schedule study visit 1 with the research staff member.

Study Visit 1 (time of enrollment):

Subjects will come to The Micheli Center for Sports Injury Prevention or Spaulding Hospital in Cambridge for a two hour visit. Once they give consent we can schedule a time for testing.

Subjects will be measured for height and weight. Subjects will complete a short medical history questionnaire, which includes the DHS, HADS, PHQ and a PCSI/ PSCC. Subjects will then be fitted for a Polar Wrist Unit and Heart Rate Monitor. During this time, they will also have a standard 5-lead ECG placed by a trained research member. Additionally, a research member will attach a blood pressure cuff to their non-dominant arm and to their middle finger (for photoplethysmographic measurements) and set up to the TCD and NIRS system. Both the usual care group and intervention group will complete this part of the study.

The first part of the study procedure involves supine rest, performing mental tasks, CO2 rebreathing, and resistance breathing to induce small periodic oscillations in arterial pressure. For resistance breathing, volunteers will breathe through a mouthpiece attached to a standard impedance threshold device made from latex-free PVC (PowerBreathe) set-up to moderate breathing resistance (10-20 cmH2O). There are no risks associated with mental or physical tasks (N-Back and finger tapping tasks) or resistance breathing. The CO2 re-breathing may cause slight lightheadedness in some people; however, this can be reversed almost immediately by switching them back to room air. Both usual care and intervention groups will complete this part of the study.

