The second part of the procedure involves the branching graded exercise test. Subjects will still be monitored using a standard 5-lead ECG and blood pressure measured by oscillometric blood pressure cuff. Throughout the graded exercise test cerebral blood flow will be monitored via TCD or NIRS. The subjects will also be connected to the metabolic cart to measure VO2. The exercise test will continue until the subject reports an increase in symptoms, using the abbreviated concussion symptom inventory or to 85% of their age-predicted maximum heart rate determined by the 5-lead ECG. The subject will be taken off the bike and cool down. Measurements will be taken for an additional five minutes. Both the usual care and intervention group will complete this part of the study.

After completion of testing, the subject will have the ECG, blood pressure cuff, metabolic cart, TCD and NIRS system removed. They will be monitored by a trained professional until symptoms ease or subject's heart rate and blood pressure has returned to resting values.

The final part of the procedure includes the single/ dual-task gait evaluation and VOMS.

Weeks 1-4 (at-home exercise):

Subjects in the intervention group will be advised to participate in aerobic exercise five days a week. This includes walking, biking, jogging and running. While participating in these activities, they will be wearing their Polar Wrist Unit and Heart Rate Monitor to help subjects track their exercise intensity. They will exercise for 20 minutes five times a week at 80% of their heart rate reverse, determined by their resting heart rate and maximum heart rate reached during exercise testing.

Usual care subjects will follow their physician's instructions for exercise and rest. They will also wear the Polar Wrist Unit and Heart Rate Monitor to track their exercise intensity, but will not receive a heart rate specific exercise recommendation.

Study Visit 2 (approximately 4 weeks post-enrollment):

All participants will participate in this visit. Subjects will undergo the same procedures as visit one, including the DHS, HADS, PHQ, PCSI/ PCSS, supine rest, graded exercise test, VOMS and

single/dual- task gait. At this time, the target heart rate for exercise will be adjusted to a new symptom limited heart rate for all participants who are still symptomatic based on the same procedure.

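### End-tidal CO2 in the exercise test is sampled only by nasal cannula while patients are on a metabolic cart, so the model's independent variable may be missing or biased

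*Combined protocol and SAP*

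**What the plan says.** - **Sampling route.** D(3) says end-tidal CO2 "will be monitored using infrared analyzer (Model 17515A, VacuMed) connected to a nasal cannula". The text names no other source.
- **When it is recorded.** According to D(3), heart rate, cerebral blood flow and end-tidal CO2 "will be recorded during a one hour session, before graded exercise test, during a graded exercise test on a cycle ergometer", and then during 5 minutes of recovery. D(5), Data collection methods, lists CO2 "levels obtained during the study session and exercise". The cannula statement therefore covers exercise.
- **The exercise test.** D(5), Schedule, Study Visit 1: "The subjects will also be connected to the metabolic cart to measure" VO2. Visits 2 and 3 repeat the visit 1 procedures.
- **A resting task.** In the resistance-breathing task of the same visit, "volunteers will breathe through a mouthpiece attached to a standard impedance threshold device".
- **The analysis.** Section H specifies one model, a linear mixed model with regional flow as outcome, end-tidal CO2 as independent variable, and symptom duration and amount of exercise as covariates. Its stated interest is the flow-CO2 relation during exercise. Section I sizes the study on that relation: 60 individuals, R² of 0.31 or higher.

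The text does not say whether the cart uses a mask or a mouthpiece, whether a nose clip is worn, whether the cannula stays in place with the cart, or how an invalid CO2 trace is recognised and handled. For blood pressure, by contrast, D(3) does change the method by phase: only the arm cuff is used during graded exercise. There is no such rule for CO2.

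**The concern.** A nasal cannula can record end-tidal CO2 only if end-expiratory gas passes the nose undiluted. Measuring VO2 requires expired gas to be collected, through either a mouthpiece or a mask. With a mouthpiece, the nose carries little or no expired gas. With a mask, a cannula may fit underneath, but its sample depends on how much the patient breathes through the mouth, which tends to increase with effort.

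Either interface can compromise the nasal sample in the phase that section H analyses. Error in the outcome would mainly add noise, but error in the independent variable goes into the coefficient itself. If the error changes with exercise intensity, recruiting more participants does not remove it, and without a trace-quality rule it may not be noticed.

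**Working it through.** **1. Does the conflict fall where the model looks?**

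- Source of CO2 in all phases: nasal cannula (D(3)).
- Exercise: CO2 recorded (D(3), D(5)) and metabolic cart connected (D(5), Visit 1).
- Model: end-tidal CO2 as independent variable, exercise as the phase of interest (sections H and I).

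The three overlap in the graded test. The resistance-breathing mouthpiece overlaps less clearly: D(5) gives that task's purpose as producing small swings in arterial pressure, and nothing places its CO2 data in the section H model.

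**2. What could the error do to the slope?** The documents contain no CO2 values or error figures, so every CO2 input below is an assumption chosen to show the range of behaviour.

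*Random error.* If recorded CO2 = true CO2 + independent noise, then

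slope recorded / slope true = SDx² / (SDx² + SDe²).

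With a true SD of 3 mmHg:
- SDe = 2: 9 / (9 + 4) = 9/13 = 0.69
- SDe = 3: 9 / (9 + 9) = 9/18 = 0.50

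*Constant proportional dilution.* If recorded = k × true, the slope is multiplied by 1/k and R² is unchanged.
- k = 0.9: 1/0.9 = 1.11
- k = 0.8: 1/0.8 = 1.25

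*Under-reading that grows with effort.* If true CO2 rises 6 mmHg over the test and the under-read grows linearly to u at peak, the recorded rise is 6 − u and the slope ratio is 6 / (6 − u).
- u = 4: 6/2 = 3.0
- u = 8: 6/(−2) = −3.0

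So the slope may shrink, grow or change sign, depending on a mechanism that the documents do not identify. The sign reverses only if the under-read exceeds the true rise.

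**3. The plan's own figure.** Section I's R² of 0.31 is the only number attached to this model. It is not reproduced by a regression F test with N = 60, α = 0.05 and power 0.8, treating the 60 individuals as independent observations: the smallest detectable R² is 0.119 with one predictor and 0.163 with three. That is a separate matter, and this point does not depend on it. It does allow a check on power. If random error with reliability λ reduces R² to 0.31 × λ, power at N = 60 falls below 0.8 only when λ is below about 0.38 (one predictor) or 0.53 (three predictors).

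**The case against.** The strongest reply is that no distortion has been shown. The cart's interface is not described, a cannula can sit under a mask, and a figure whose content is not available stands just before the CO2 sentence in D(3), so an interface shown there cannot be excluded. The possible mechanisms also differ. A mouthpiece with a nose clip would give a flat, visibly invalid trace, that is, missing data; under-reading that grows with effort needs free breathing through nose and mouth, as under a mask. The threefold and sign-reversal figures belong only to the second case, and their inputs are all assumed. This stands, and it limits the claim to a predictor that may be missing or biased. It does not remove the point, because each plausible interface poses a problem for a nasal sample, and the text gives no alternative route and no quality rule.

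A reader might go further in three ways that the documents do not support:

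- **Bias by arm or visit.** The section H model has no arm or visit term, and both arms undergo the same test with the same stopping limits. Nothing in the documents shows that the error differs between arms or visits.
- **Loss of power.** By the calculation above, power against the plan's R² holds unless reliability is quite low. Bias in the slope is the issue.
- **Damage to the trial's endpoints.** The primary endpoint in D(4) is prefrontal blood oxygenation before and after the exercise protocol, and the secondary concerns persisting symptoms. Neither is defined with CO2.

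**Conclusion.** The point holds as a mismatch between the stated measurement method and the conditions of use. End-tidal CO2 is the independent variable of the only specified model, and its only stated source is a nasal cannula during a test in which expired gas must be collected for VO2. The predictor may therefore be missing or biased during exercise.

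Neither the size nor the direction of the slope bias can be determined from the documents. The illustrative slope ratios run from 0.50 to 3.0 and include a reversal to −3.0; they rest wholly on assumed values and are not estimates for this trial. The conclusion itself rests on one technical premise, that VO2 measurement needs a mask or mouthpiece.

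The resistance-breathing mouthpiece is secondary, since its CO2 data are not clearly used in the model. The change should be made, because it is cheap and protects the coefficient that section H is built on, but the D(4) endpoints do not depend on it.

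**What to change.** **D(3).** During the graded test, the rest immediately before it and the recovery after it, connect the existing infrared analyzer's sampling line to the mask or mouthpiece port, or use the cart's own CO2 channel if it has one. One sampling site then covers the whole contrast analysed. Keep the nasal cannula for phases without a breathing circuit. State the interface for each phase, including CO2 rebreathing and resistance breathing.

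**Section H.** State that the exercise model uses the circuit-sampled values. Exclude CO2 traces without a valid end-expiratory plateau, and report how many are excluded. Flag participants already tested with the cannula.

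**Cost.** A sampling-line adapter and a few sentences of protocol text. The interface has to be in place before exercise starts and stay on through the 5 minutes of recovery. CO2 values from cannula phases and circuit phases will not be directly comparable, so the two should not be pooled in one slope. If the site already samples from the circuit, a sentence in D(3) and one in section H settle the sampling site, and only the trace-quality rule remains to be added.
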